4.1.2 Secondary Endpoints

All endpoints achieved within 30 day period after end of study drug treatment:

- Number of subjects with complete remission (defined as confirmed platelet response and absence of exacerbation)
- Number of (subjects with) exacerbations of TTP (defined as recurrent thrombocytopenia following a confirmed platelet response and requiring a re-initiation of daily PE treatment after ≥ 1 day but ≤ 30 days after the last daily PE) and time to first exacerbation of TTP
- Number of subjects relapsing of TTP (defined as *de novo* event of TTP that occurs later than 30 days after the last daily PE)
- Number of daily PE sessions, number of plasma units administered and number of days of daily PE
- Resolution of non-focal neurological symptoms as defined by neurocognitive function at complete remission, measured by a neurocognitive test battery
- Resolution or improvement (improvement of ≥ 1 grade in the CTCAE v4.0 scale) of TTP-related signs and symptoms as captured on physical examination and as adverse events, at complete remission and at end of the study drug treatment period (including tapering) (by number of unique subjects and by total number of AEs)
- Total mortality within the PE treatment period and within the subsequent study drug treatment period (including tapering)
- Incidence of PE treatment-related AEs, such as, but not restricted to: haemorrhage from catheter insertion, sepsis, catheter thrombosis, pneumothorax, fluid overload, hypoxia, hypotension, anaphylactoid reactions and TRALI

- Incidence and severity of ALX-0081 treatment-emergent AEs and relationship to study drug
- Development of ADA \leq 30 days post-last study drug treatment
- PK and PD profile

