4.3 Overview of Treatment and Dosing Regimen for Study Drug

The primary treatment for acquired TTP is daily PE. Immunosuppressive treatment is also often administered. The centres will follow their respective guidelines for the treatment of TTP patients, regarding all items other than the study drug. Discontinuation of daily PE depends on normalisation of platelet count, neurological status and other clinical and laboratory parameters. The frequency of PE is occasionally reduced ('tapered') rather than stopping completely at time of response, however this is not based on randomised clinical trial data and is not recommended per this protocol (although it is allowed if considered necessary by the Investigator).

The study drug will be administered as adjunctive treatment at specific times relative to the PE procedures.

The first administration is a single i.v. bolus injection, administered by a push injection. All subsequent administrations are s.c. injections. The study drug consists of 10 mg of ALX-0081 or placebo, once daily (except if PE is given twice daily, then study drug is 10 mg twice daily) as described in Section 7.2.

Note that, in case of re-initiation of daily plasma exchange due to exacerbation, no i.v. bolus injection will be administered prior to the first new PE session; daily s.c. study drug administration will continue per protocol.

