7.2 Treatment and Dosing Regimen for Study Drug

The study drug will be administered as adjunctive treatment at specific times relative to the PE procedures. The study drug consists of 10 mg of ALX-0081 or placebo, once or twice daily as explained below (Table 8).

Subjects will receive a first i.v. bolus of 10 mg ALX-0081 or placebo via push injection within 6h, but not later than 15 min prior to the initiation of PE on study (i.e., the very first PE session, if the subject was randomised prior to the initiation of PE, or the second PE session, if the subject was randomised after one, single PE session; see section 4.2). This first PE on study is followed by s.c. administration of 10 mg study drug within 30 minutes after the end of the PE procedure.

During the complete PE treatment period (including tapering and PE given for exacerbations), study drug will be administered daily via s.c. injections.

- If 1 PE per day is scheduled, 10 mg of study drug will be administered within 30 minutes after the end of the PE procedure.
- If 2 PEs per day are scheduled, 10 mg of study drug will be administered within 30 minutes after the end of each PE procedure. The maximum total daily dose of study drug is hence 20 mg.
- If less than 1 PE per day is scheduled (i.e. during a tapering regimen), 10 mg of study drug will be administered daily. On days with a PE, study drug administration should be within 30 minutes after the end of the PE procedure; on days without PE, study drug administration should be 24 h (\pm 1 h) after previous administration

Daily s.c. study drug administration of 10 mg will continue for 30 days after the very last PE (including tapering).

Maximum treatment duration with study drug will be limited to 90 days after first administration of study drug.

In case of exacerbation of TTP (after \geq 1 day but \leq 30 days after the last daily PE), standard treatment (PE) should be re-initiated and daily s.c. administration of study drug continued.^a The “study drug post-PE” period (for 30 days after the very last PE, see Figure 5 further below) will re-commence once PE is again stopped. Maximum treatment duration with study drug will be limited to 90 days after first administration of study drug.

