7.5 Assignment to Treatment

Subjects will be assigned to one of the two treatments according to a computerised randomisation schedule. When the randomisation number and treatment assignment are obtained, the randomisation number will be recorded on the CRF. This is a single blinded study. The Investigator will be informed of the treatment at the time of randomisation.

Randomisation is performed via an interactive web-based system.

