The number and percentage of unique subjects with resolved or improved TTP-related signs and symptoms as captured on physical examination and as adverse events within the PE treatment period, within the ensuing 30 days and at the one month follow-up will be summarised by treatment and overall along with the exact binomial CI of the percentage. Improvement of physical examination is defined as progressing from an abnormal to a normal result for a particular system at a given time point. Resolution of physical examination is defined as having normal results for all systems at a given time point. Resolution of an adverse event is defined as having a stop date present and an outcome of either 'resolved' or 'resolved with sequelae' within the given period. Both physical examination systems and adverse events flagged as being related to TTP will be considered.

The number and percentage of deaths within the PE treatment period, within the ensuing 30 days (study treatment period) and within the period from the end of the study treatment period up to and including the one month follow-up will be presented for each treatment group and overall for the ITT population only. Each death will be categorised into one of the distinct periods identified above, such that the death is counted only once in the table.

The incidence of PE treatment-related AEs, such as, but not restricted to: hemorrhage from catheter insertion, sepsis, catheter thrombosis, pneumothorax, fluid overload, hypoxia, hypotension, anaphylactoid reactions and transfusion related acute lung injury (TRALI) will be summarised by system organ class, preferred term, treatment group and overall. The summary will be repeated for PE treatment-related SAEs for the ITT population only.

---

Frequency tables (with accompanying Chi-square p-values) will be made for the following characteristics: use of corticosteroids during daily PE, use of rituximab during daily PE and tapering. Use of corticosteroids will be determined by using the Concomitant Medications data (both PE related and not PE related) with ATC codes beginning with “H02” (systemic corticosteroids). Use of rituximab will be determined by using the Concomitant Medications data (both PE related and not PE related) with ATC code “L01XC” (coded term “RITUXIMAB”).

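### The PE-period death count runs over a window that ends with platelet response, so it is expected to favour ALX-0081 even without a survival effect; add ITT mortality at a fixed time from randomisation

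*Protocol*

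**What the plan says.** Reducing mortality is a secondary objective (protocol 3). The endpoint in protocol 4.1.2 is "Total mortality within the PE treatment period and within the subsequent study drug treatment period (including tapering").

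SAP 6.3.2 turns this into a table for the ITT population: "The number and percentage of deaths within the PE treatment period, within the ensuing 30 days (study treatment period"), followed by deaths "within the period from the end of the study treatment period up to and including the one month follow-up". The rows are exclusive: "Each death will be categorised into one of the distinct periods identified above, such that the death is counted only once in the table".

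Three other provisions set the length of these windows:

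- **End of daily PE** (protocol 4.3): "Discontinuation of daily PE depends on normalisation of platelet count, neurological status and other clinical and laboratory parameters". The person managing PE knows the assignment (protocol 7.5): "The Investigator will be informed of the treatment at the time of randomisation".
- **Post-PE drug period** (protocol 7.2): "Daily s.c. study drug administration of 10 mg will continue for 30 days after the very last PE (including tapering"). It restarts after an exacerbation.
- **Overall cap** (protocol 7.2): "Maximum treatment duration with study drug will be limited to 90 days after first administration of study drug".

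The PE period is not described in one way. Protocol 4.1.2 and SAP 6.3.2 speak of the PE period. Protocol 8.2.1 and SAP 4 speak of the daily PE period, and SAP 4 assigns tapering to the later study-drug period.

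**The concern.** A death count compares arms fairly only if both arms are exposed for the same time. Here the first window closes at an event closely tied to the primary endpoint. An arm that recovers platelets sooner leaves the window sooner, and a later death is booked in another row. The PE-period row would then partly restate the primary result while being labelled mortality.

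At stake is how a stated mortality objective is read, in a disease for which protocol 2.5.2 cites 10% to 30% mortality per acute bout. A lower PE-period count could be taken as a survival signal when it shows only a shorter PE course.

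**Working it through.** **The plan's own figure.** The documents give no expected number of deaths. The planning medians (6 and 3.36 days, protocol 10.4) are the relevant inputs, and they reproduce the stated sample size. Events = 4 × (1.960 + 0.842)² / [ln(6/3.36)]² = 93.4, and 93.4 / 0.85 = 109.9, i.e. 110 subjects.

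**Quick check.** Take the same constant daily death hazard in both arms, set so that 10% die over 36 days (a 6-day PE course plus 30 days): h = −ln(0.9)/36. With an exponential PE length, the mean is median/ln 2. Expected PE-period deaths per 55 subjects:

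- Placebo: 55 × h × 6/ln 2 = 1.39
- ALX-0081: 55 × h × 3.36/ln 2 = 0.78
- Ratio: 3.36/6 = 0.56

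**All windows, base case.** Inputs: 10% mortality by day 30, so h = −ln(0.9)/30 = 0.00351 per day in both arms; PE ends at response at rate λ = ln 2/median (0.1155 and 0.2063 per day); the third window is taken as 30 days.

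- PE period: p₁ = h/(h + λ)
- Ensuing 30 days: p₂ = (1 − p₁) × 0.10
- Next 30 days: p₃ = (1 − p₁) × 0.90 × 0.10

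| Window | Placebo | ALX-0081 | Ratio |
|---|---|---|---|
| PE period | 2.95% (1.6 per 55) | 1.67% (0.9 per 55) | 0.57 |
| Ensuing 30 days | 9.70% | 9.83% | 1.01 |
| First two windows | 12.66% | 11.51% | 0.91 |
| All three windows | 21.39% | 20.36% | 0.95 |
| Fixed day 30 | 10% | 10% | 1.00 |

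Survival is identical by construction, so every departure from 1.00 comes from the windows.

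**Range.** The calculation was repeated over 32 combinations, with no survival effect in any of them:

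- PE length: the planning medians, or means of about 16 and 9 days. The 16 is the average number of daily treatments in protocol 2.5.2, and 16 × 0.56 ≈ 9.
- Lag from response to end of PE: 0 or 2 days.
- Death hazard: constant, or front-loaded (Weibull shape 0.5).
- 30-day mortality: 5%, 10%, 20% or 30%.
- PE truncated at 60 days, so that PE plus 30 days stays within the 90-day cap.

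ALX-0081/placebo ratios:

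- PE period: 0.56 to 0.84 (0.75 to 0.84 when the hazard is front-loaded)
- Ensuing 30 days: 1.01 to 1.16
- First two windows combined: 0.86 to 0.96
- All three windows: 0.92 to 0.98

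Expected placebo PE-period deaths run from 0.8 to 12 per 55. ALX-0081 would show fewer PE-period deaths than placebo in 41% to 80% of such trials, and more in 13% to 32%; the rest are ties.

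**The case against.** Most of the opposing case is sound.

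- **The study-drug window.** A reader might infer that the drug shortens every mortality window. It does not. The post-PE window is 30 days in both arms; faster response moves it earlier, and with equal survival it shows slightly more deaths on ALX-0081.
- **Visibility.** The three SAP windows are contiguous and each death is counted once, so a reader can add the rows and see the shift. The sum is biased by only about 2% to 8%.
- **Certainty.** A reader might infer that ALX-0081 will show fewer PE-period deaths. That holds only in expectation and only if PE is in fact shortened, which is the trial's hypothesis.
- **Size.** A 44% reduction might be taken as the answer. It needs a constant hazard and PE ending at response; with a front-loaded hazard the reduction is 16% to 25%.
- **No formal inference.** Protocol 10.6 makes secondary endpoints descriptive, and SAP 6.3.2 calls secondary p-values exploratory.
- **Another death count exists.** SAP 6.4.1 tabulates subjects with treatment-emergent events whose outcome is death, from first dose and with no stated end. This weakens any claim that mortality appears only in response-dependent windows. It does not close the gap. It uses the safety population and is not a time-to-event estimate. Protocol 9.1.6 also ends the treatment-emergent period 30 days after study drug, which would again tie it to the end of treatment.
- **Redaction.** The tertiary, longer-term and exploratory sections (protocol 4.1.3 and 10.7; SAP 6.3.5 and 6.3.6) are blacked out and could contain a fixed-time analysis.

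What survives is the PE-period row, and the lack of an equal-time ITT mortality estimate in the readable text.

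**Conclusion.** The point holds in limited form. If ALX-0081 shortens PE, the PE-period row is expected to favour it with no survival benefit, at a ratio of about 0.56 to 0.84. Over longer spans the distortion shrinks to 4% to 14% and then 2% to 8%. A reader might go further and conclude that the planned mortality analysis as a whole is invalid, or that a formal claim is compromised. The documents do not support that: all windows are reported, the total is nearly unbiased, and no confirmatory test is planned. This is a cheap improvement, not a flaw that threatens the trial's conclusions.

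Assumptions not in the documents are the exponential PE length, the lag, the hazard shapes, the 5% mortality case, reading 10% to 30% as 30-day mortality, and PE ending independently of death risk. If risk fell because faster disease control ended PE, that would be a real survival effect and outside this point. Exacerbations are ignored. They restart the post-PE drug period, so a difference between arms in exacerbations could also make the windows unequal.

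**What to change.** In SAP 6.3.2, make the main mortality comparison all-cause mortality from randomisation at day 30 in the ITT population: Kaplan-Meier estimates by arm with 95% CIs, and the arm difference with its CI. Day 30 suits the first formal analysis, which uses data to the one-month follow-up (SAP 6.6), about day 66 after a 6-day PE course (6 + 30 + 30). Add day 90, either with censoring at that analysis or at the end-of-study analysis.

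Keep the three-window table as description and give it a total row. State one definition of the PE period, reconciling protocol 4.1.2 and SAP 6.3.2 with protocol 8.2.1 and SAP 4, including where tapering falls. A clock from randomisation also covers randomised subjects who were never dosed, who are in the ITT population but have no study-drug period.

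The cost is one extra table and no new data: SAEs, including fatal ones, are reported to one year or withdrawal (protocol 9.2.2.3). The downside for the sponsor is a mortality contrast that may look less favourable than the PE-period row.

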4.1.3 Tertiary Endpoints

[REDACTED]

- [REDACTED]
- [REDACTED]
- [REDACTED]

4.2 Overall Study Design

This is a Phase II multicentre, single-blinded, parallel design, randomised, placebo-controlled study. The study population is symptomatic patients with acute episodes of acquired TTP, requiring treatment with PE. After confirmation of eligibility to study participation, subjects will be randomised in a ratio of 1:1 to either receive ALX-0081 or placebo as adjunctive therapy to PE (Figure 4). Subjects will be randomised prior to the start of PE treatment. In exceptional cases however (due to need or ability to start PE in a time frame which does not allow all required screening and/or baseline study procedures to be performed), a subject may be randomised after the first, single PE session, but prior to the start of the second PE session. This overall second PE session should be started within 24 hours of the end of the very first PE session, and will be considered the first PE on study.

The subjects will be followed in different phases during this study (also see Figure 5):

- Screening and baseline measurements after admission to hospital
- Treatment phase
 - Single i.v. bolus study drug administered via push injection
 - Daily PE adjunctive s.c. treatment phase
 - Post-daily PE s.c. treatment phase (including PE tapering if applicable, and study drug post-PE for 30 days after the very last PE)
- Follow-up phase

Laboratory parameters for inclusion, study conduct, safety assessments and assessments of response/relapse, re-treatment and study medication dose modification will be assessed at each local site laboratory.

[figure not shown]

Figure 4: Treatment flow chart.
First PE on study: see section 4.2

4.3 Overview of Treatment and Dosing Regimen for Study Drug

The primary treatment for acquired TTP is daily PE. Immunosuppressive treatment is also often administered. The centres will follow their respective guidelines for the treatment of TTP patients, regarding all items other than the study drug. Discontinuation of daily PE depends on normalisation of platelet count, neurological status and other clinical and laboratory parameters. The frequency of PE is occasionally reduced ('tapered') rather than stopping completely at time of response, however this is not based on randomised clinical trial data and is not recommended per this protocol (although it is allowed if considered necessary by the Investigator).

The study drug will be administered as adjunctive treatment at specific times relative to the PE procedures.

The first administration is a single i.v. bolus injection, administered by a push injection. All subsequent administrations are s.c. injections. The study drug consists of 10 mg of ALX-0081 or placebo, once daily (except if PE is given twice daily, then study drug is 10 mg twice daily) as described in Section 7.2.

Note that, in case of re-initiation of daily plasma exchange due to exacerbation, no i.v. bolus injection will be administered prior to the first new PE session; daily s.c. study drug administration will continue per protocol.

4.4 Study Duration

The anticipated recruitment period is 30 months. The maximum total duration of individual study participation is a maximum of 15 months: a treatment phase of up to 90 days and a follow-up period of maximum of 1 year after remission or after 90 days of treatment, whichever comes first. Subjects will be hospitalised for at least 1 day after the last daily PE.

4.5 DSMB and Premature Termination of the Study

4.5.1 Data Safety Monitoring Board

An independent DSMB will monitor accruing safety data during the study (SAEs on an ongoing basis and 'early safety look' when 16 subjects, 8 ALX-0081 treated and 8 placebo treated, have completed treatment with study drug) and will make recommendations on continuation of the study as appropriate. An interim analysis for safety with formal stopping

rules is foreseen when 28 of the ALX-0081 treated subjects have been treated, and will make a recommendation on study continuation or discontinuation. No formal review of efficacy data by the DSMB is foreseen.

4.5.2 Premature Termination of the Study

The Sponsor in consultation with the DSMB and the CRO has the right to terminate the study prematurely for safety reasons. In addition, the Sponsor may terminate the study prematurely for administrative reasons at any time. In all cases all necessary measures have to be taken to guarantee appropriate safety follow-up of all subjects already included in the study.

The Independent Ethics Committees (IEC) or Institutional Review Board (IRB) and the Regulatory Authorities will be informed in writing about any premature termination of the study.

5. SELECTION AND WITHDRAWAL OF SUBJECTS

The target population for this trial includes symptomatic patients with acute episodes of acquired TTP, requiring treatment with PE.

5.1 Inclusion Criteria

1. 18 years of age or older
2. Men or women willing to accept an acceptable contraceptive regimen
3. Patients with clinical diagnosis of TTP
4. Necessitating PE (one, single PE session prior to randomisation into the study is allowed)
5. Subject accessible to follow-up
6. Obtained, signed and dated informed consent

5.2 Exclusion Criteria

1. Platelet count greater or equal to 100,000/ μ L
2. Severe active infection indicated by sepsis (requirement for pressors with or without positive blood cultures)
3. Clinical evidence of enteric infection with *E. coli* 0157 or related organism
4. Anti-phospholipid syndrome
5. Diagnosis of DIC
6. Pregnancy or breast-feeding
7. Haematopoietic stem cell or bone marrow transplantation-associated thrombotic microangiopathy
8. Known congenital TTP
9. Active bleeding or high risk of bleeding
10. Uncontrolled arterial hypertension
11. Known chronic treatment with anticoagulant treatment that can not be stopped safely, including but not limited to:
 - vitamin K antagonists
 - heparin or LMWH
 - non-acetyl salicylic acid non-steroidal anti-inflammatory molecules
12. Severe or life threatening clinical condition other than TTP that would impair participation in the trial

13. Subjects with malignancies resulting in a life expectation of less than 3 months
14. Subjects with known or suspected bone marrow carcinosis
15. Subjects who cannot comply with study protocol requirements and procedures.
16. Known hypersensitivity to the active substance or to excipients of the study drug
17. Severe liver impairment, corresponding to grade 3 toxicity defined by the CTCAE scale. For the key liver parameters, this is defined as follows:
 - bilirubin > 3 x ULN (need to differentiate isolated increase in indirect bilirubin due to haemolysis, this is not an exclusion parameter but disease related)
 - ALT/AST > 5 x ULN
 - AP > 5 x ULN
 - gamma glutamyl transpeptidase (GGT) > 5 x ULN
18. Severe chronic renal impairment, as defined by GFR < 30 mL/min

5.3 Participation in concurrent clinical trials

The use of another investigational drug or device within 30 days prior to screening is not allowed. Participation in non-interventional/observational studies and registries during the study period is allowed. Participation in another clinical trial is not allowed until the end of the follow up period or within 30 days after the last study treatment in case of early subject withdrawal from the study. Subjects that already participated in the current study (ALX 0681-2.1/10) and that have either completed the study per protocol or have discontinued prematurely, are not allowed to be re-included.

